11.0 Statistical Considerations

Accrual: Annually, 420 new patients receive chemotherapy at DFCI and 120 at UAB. Based on prior institutional HMH data, we estimate 20% will be eligible to participate at DFCI (N=84) and 30% will be eligible to participate at UAB (N=36). We estimate a 75% consent rate for a total possible annual sample size of N=90 patients (63 DFCI, 27 UAB). Forty patients will be accrued over 6-months at DFCI (n=28) and UAB (n=12). Patients will be randomized 1:1 by site to PediCARE versus UC.

Analysis Plan: Sample demographic, disease, treatment and utilization variables from the survey instruments and medical chart will be described by summary statistics.

The rate of consent to randomized intervention and the 6-month completion will be estimated along with a 90% confidence interval (CI). Feasibility will be established if the upper bound of the CI contains 75% and 80% for consent and follow-up respectively. With an estimated 60 eligible patients at 6 months, at least 39 (65%; 90% CI 53.6-75.2%) need to enroll for the upper bound of the 90% CI contain 75%. With an estimated 40 randomized patients, at least 28 (70%; 90% CI 56.0-81.7%) need to have complete 6-month data to have the upper bound of the 90% CI contain 80%. The 6-month completion rate will also be estimated along with a 90% CI by randomized arm (PediCARE and UC).

For each family, the difference between 6-month and baseline HMH scores will be categorized as improved (change score <0) or not improved (change score ≥0). For each arm, the proportion of families with improved HMH at the completion of the intervention (6-months) will be estimated along with a 90% exact CI. Based on prior data, we assume a 30% resolution in HMH in UC, thus the 90% CI will be within ±24.9%. For each arm, the per patient number of ED visits and ICU stays will be summarized (median, range). The proportion of patients with at least one ED and/or ICU visit will be estimated for each arm, as well as the difference between arms, along with a 90% confidence interval. Additionally, the rate of HMH at the completion of the intervention pilot (6-months) along with a 90% exact confidence will be estimated for UC and PediCARE. For the PediCARE arm, the cost per patient, study team contact hours, and proportion with successful receipt of all intervention components will be described overall and by site.

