2.0 Objectives

2.1 Overall Study Objectives:

The overarching goal of this study is to pilot a randomized controlled trial (RCT) of the Pediatric Cancer Resource Equity (PediCARE) intervention to determine feasibility of intervention administration in a childhood cancer population. Secondary goals include generation of effect size estimates for a primary endpoint of reduction in household material hardship (HMH) and a secondary endpoint of Emergency Department and Intensive Care Unit utilization to support

planning of a subsequent definitive multi-center RCT. PediCARE is a poverty-targeted intervention utilizing direct resource provision of groceries and transportation.

2.2 Specific Aims:

Pilot RCT to determine feasibility

To conduct a pilot RCT of the PediCARE intervention in 40 newly diagnosed pediatric cancer families with HMH at DFCI and UAB. Families in the intervention arm will receive PediCARE for 6-months. The control group will receive usual care. Data will be collected by parent survey at baseline and 6-months. The primary outcome will be defined as feasibility. Secondary outcomes will include improvement in HMH scores (range 0-4) at 6-months compared to baseline and Emergency Department (ED) and Intensive Care Unit (ICU) admissions. Analyses will focus on effect size estimates to plan a subsequent RCT.

H2a. Feasibility will be demonstrated by recruitment rate of 75% and follow-up survey data collection of 80% per arm.

H2b: There will be a trend towards a reduction in HMH scores (primary endpoint) and lower proportion of patients experiencing an ED visit or ICU admission over 6-months in the PediCARE versus usual care group.

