4.0 Planned Enrollment

This study aims to enroll a total of 40 participants as follows:

Pilot RCT DFCI and UAB: The target sample size is 40 participants. At DFCI, a total of 28 participants will be enrolled and randomized (thus 14 participants will receive PediCARE and 14 participants will receive UC). At UAB a total of 12 participants will be enrolled and randomized (thus 6 participants will receive PediCARE and 6 participants will receive UC).

Families will be recruited consecutively at each site over a 6-month time period. Patients will be randomized 1:1 to PediCARE versus Usual Care (UC) and randomization will be stratified by site.

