8.0 Study Endpoints

8.1 Feasibility: The primary endpoint of this study is feasibility. Feasibility will be defined as at least 75% consent to randomization and at most 20% attrition per arm. We will assess process barriers to feasibility including recruitment, attrition by arm and parent report of PediCARE component utilization (i.e. food and transportation).

[figure not shown]
Study Timeline (Months)	Months 1 -6 Year 1	Months 7- 12 Year 1	Months 1-6 Year 2
Screen and enroll families (6 months)			
Intervention administration (6 months)			
Data analysis			

8.2 HMM and Utilization: The secondary endpoints of this study will be used to generate effect size estimates to support planning of a subsequent RCT. Secondary endpoints will be evaluated comparing recipients of PediCARE versus Usual Care. Secondary outcomes include change in HMM utilizing an HMM score (range 0-4) at 6-months compared to baseline; and proportion of patients experiencing an Emergency Department (ED) visit or Intensive Care Unit (ICU) admission over 6-months.

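### The Section 11 rule for the primary endpoint accepts 65% consent and 70% pooled completion, whereas Section 8.1 and H2a require 75% and 80% in each arm

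*Combined protocol and SAP*

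**What the plan says.** Section 8.1 states that "The primary endpoint of this study is feasibility" and then defines it: "Feasibility will be defined as at least 75% consent to randomization and at most 20% attrition per arm". Hypothesis H2a in Section 2.2 agrees: "Feasibility will be demonstrated by recruitment rate of 75% and follow-up survey data collection of 80% per arm". Neither mentions a confidence interval.

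The Analysis Plan in Section 11.0 gives a different rule, based on 90% confidence intervals: "Feasibility will be established if the upper bound of the CI contains 75% and 80% for consent and follow-up respectively". It then states the minimum counts. For consent: "With an estimated 60 eligible patients at 6 months, at least 39 (65%; 90% CI 53.6-75.2%) need to enroll". For follow-up: "With an estimated 40 randomized patients, at least 28 (70%; 90% CI 56.0-81.7%) need to have complete 6-month data". The follow-up count covers both arms together. On the arms separately it says only: "The 6-month completion rate will also be estimated along with a 90% CI by randomized arm (PediCARE and UC)". No threshold is attached to the by-arm estimates.

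On size, Section 4.0 says "The target sample size is 40 participants", with 14 + 6 = 20 families in each arm across the two sites.

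**The concern.** The two rules differ in two respects.

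- **Threshold.** Section 8.1 sets 75% consent and 80% completion. Section 11 asks only that the upper limit of a 90% interval reach those values. That shows the data are compatible with the target, not that it was met, so the claim that feasibility is established does not follow. Such a rule also becomes easier to satisfy as the sample shrinks and the interval widens.
- **Unit.** Section 8.1 and H2a apply the follow-up criterion in each arm. Section 11 applies it to the pooled 40, so good retention in one arm can offset poor retention in the other. The trial is unblinded and only one arm receives groceries and transport, so unequal attrition is a plausible way for it to fail.

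At stake is the verdict on the primary endpoint, and with it the case for the multi-center trial that the pilot is meant to support. With two unreconciled rules, the verdict could be chosen after the data are seen.

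**Working it through.** **Inputs.** Targets of 75% consent and 80% completion (Sections 2.2, 8.1, 11). Denominators of 60 eligible and 40 randomized (Section 11). 20 per arm (Section 4.0). 90% two-sided intervals (Section 11). The method is not named for these two rates, but the exact (Clopper-Pearson) interval reproduces the printed limits.

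**Step 1: reproduce the plan's figures.** The exact upper limit for x of n is the 95th percentile of Beta(x+1, n−x).

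| Count | Rate | Exact 90% CI | Upper limit reaches target? |
|---|---|---|---|
| 38/60 | 63.3% | 51.9–73.7% | no (75%) |
| 39/60 | 65.0% | 53.6–75.2% | yes |
| 27/40 | 67.5% | 53.4–79.6% | no (80%) |
| 28/40 | 70.0% | 56.0–81.7% | yes |

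Both stated minima and both intervals are correct. The arithmetic is not at fault.

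**Step 2: set the rules side by side.** Read as observed rates, Section 8.1 needs 0.75 × 60 = 45 consents and 0.80 × 20 = 16 completers in each arm.

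- 28/40 is 30% attrition, against a maximum of 20%.
- Every pooled total from 28 to 31 passes Section 11 and must fail 8.1, because 16 + 16 = 32.
- Totals of 32 to 35 can also fail 8.1; 20 + 15 is one case.
- 20/20 with 8/20 totals 28 and passes Section 11 with 60% attrition in one arm. That arm's own exact upper limit is 60.6%, which excludes 80%.

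**Step 3: consent when enrolment stops at 40.** 40/53 = 75.5% meets 8.1 and 40/54 = 74.1% does not. Section 11 still passes at 40/61 (upper limit 75.6%) and fails at 40/62 (74.6%). The rules therefore disagree for every eligible count from 54 to 61. That range includes Section 11's estimate of 60, where 40/60 = 66.7% (upper limit 76.7%).

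**Step 4: probability of passing.** Consent and completion are treated as independent binomials.

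- Section 11: P(X≥39 | 60) × P(Y≥28 | 40)
- Section 8.1: P(X≥45 | 60) × P(Y≥16 | 20)²

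| True consent / completion | Section 11 | Section 8.1, per arm |
|---|---|---|
| 65% / 70% | 0.559 × 0.577 = 0.323 | 0.066 × 0.056 = 0.004 |
| 70% / 75% | 0.838 × 0.821 = 0.688 | 0.244 × 0.172 = 0.042 |
| 75% / 80% | 0.970 × 0.957 = 0.928 | 0.569 × 0.397 = 0.226 |
| 80% / 85% | 0.998 × 0.996 = 0.994 | 0.869 × 0.689 = 0.599 |

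At 70%/75%, a pooled version of 8.1 (32/40) would pass 0.244 × 0.300 = 0.073, so most of the gap comes from the threshold when the arms are alike.

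The 45-of-60 criterion implies more enrolments than the target of 40. If enrolment instead stops at 40, Section 11 passes on consent with at most 61 eligible and 8.1 with at most 53. The joint probabilities become 0.669 against 0.041 at 70%/75%, and 0.922 against 0.215 at 75%/80%.

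**Step 5: unequal arms, follow-up criterion only.** With true completion of 90% in one arm and 60% in the other:

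| Criterion | Probability of passing |
|---|---|
| Pooled 28/40 | 0.836 |
| 16/20 in each arm | 0.957 × 0.051 = 0.049 |
| Interval rule by arm, 13/20 in each (65%; 44.2–82.3%) | 0.416 |

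**The case against.** The best defence is that 8.1 and H2a state targets, while Section 11 says how a small sample is judged against them: feasibility is rejected only if the data exclude the target at a one-sided 5% level. Section 11 prints its minimum counts openly, and 8.1 does not say that observed rates decide. Leniency also has a reason: under the strict reading, a study with true rates exactly on target passes only about 23% of the time.

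This stands as a case for a lenient rule in a 40-family pilot. It does not make a limit that merely fails to exclude the target into proof that the target was met, and it leaves the pooled versus per-arm mismatch untouched.

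Two further points have some weight. First, 40 of 60 is not the plan's consent forecast. At its assumed 75%, enrolment would fill at about 40/0.75 ≈ 53 eligible families, and 40/53 passes both rules. The 54-to-61 range therefore shows where the rules part, not what the plan expects. Second, completion will be reported by arm, so readers would see an imbalance, and the 20 + 8 and 90%/60% examples are extreme. Reporting would still not change the Section 11 verdict.

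**Conclusion.** The concern holds. Section 11 can declare the primary endpoint met on data that Section 8.1 and H2a call not feasible, and no section says which rule takes precedence. With true rates five points below both targets, the pass probability is about 69% under Section 11 and 4% under 8.1, or 67% and 4% if enrolment stops at 40, so the result does not depend on the denominator of 60. These figures assume 20 families per arm, independence of consent and completion, and 8.1 read as a rule on observed rates. The contradiction in the text, 30% pooled attrition accepted against a 20% per-arm maximum, needs none of these assumptions. It should be corrected before the primary endpoint is analysed.

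**What to change.** State one rule in Sections 2.2, 8.1 and 11. The choice is the sponsor's.

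- **(a) Decide on observed rates.** Require consent of at least 75% and completion of at least 80% in each arm (16/20), and report the 90% intervals as precision only. Section 8.1 names no denominator for consent, so define one. Eligible families identified up to the close of enrolment would serve, provided the text says how families not yet approached are counted.
- **(b) Keep the interval rule.** Word the conclusion as rates of 75% and 80% not being ruled out. Either apply the follow-up criterion by arm (13/20) or state that it is pooled. Amend 8.1 and H2a to say that observed rates of about 65% consent and 70% completion (65% if by arm) satisfy it.

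Either is a wording amendment needing IRB approval, with no new data, visits or patients.

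The price of (a) is strictness: it passes about 23% of the time at true rates of exactly 75%/80% and about 60% at 80%/85%, against 93% and 99% under Section 11 now.

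The price of (b) is a weaker conclusion. Applied by arm, it stays lenient when both arms fall short equally (0.838 × 0.807 = 68% at 70%/75%), though it cuts the follow-up pass rate in the 90%/60% case from 84% to 42%.

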Participating institutions will be required to participate in monthly Coordinating Center initiated teleconferences.

Remote Monitoring will be performed by central monitoring of REDCap survey completion (data are electronically entered and stored thus source verification is non-applicable unless paper/pencil survey administered due to technological challenges in which case these will be scanned and securely emailed to DFCI for central data entry and source documentation).

Monitoring Reports

The DF/HCC Sponsor will review all monitoring reports to ensure protocol compliance. The DF/HCC Sponsor may increase the monitoring activities at Participating Institutions that are unable to comply with the protocol, DF/HCC Sponsor requirements or federal and local regulations.

Accrual Monitoring

Prior to extending a protocol to an external site, the DF/HCC Sponsor will establish accrual requirements for each participating institution. Accrual will be monitored for each participating institution by the DF/HCC Sponsor or designee. Sites that are not meeting their accrual expectations may be subject to termination.

Accrual expectations for University Alabama Birmingham are as follows: Enrollment of 12 participants over 12 months.

AUDITING: QUALITY ASSURANCE

Auditing is a method of Quality Assurance and involves the systematic and independent examination of all trial related activities and documents. Audits determine if evaluated activities were appropriately conducted and whether data was generated, recorded and analyzed, and accurately reported per the protocol, applicable Policies, and the Code of Federal Regulations (CFR).

DF/HCC Internal Audits

All Participating Institutions are subject to audit by the DF/HCC Office of Data Quality (ODQ). Typically, approximately 3-4 participants would be audited at the site over a 2-day period. If violations which impact participant safety or the integrity of the study are found, more participant records may be audited.

Audit Notifications

It is the Participating Institution's responsibility to notify the Coordinating Center of all external audits or inspections (e.g., FDA, EMA, NCI) that involve this protocol. All institutions will forward a copy of final audit and/or re-audit reports and corrective action plans (if applicable) to the Coordinating Center, within 12 weeks after the audit date.

Audit Reports

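### The plan has two different pass rules for its primary feasibility endpoint; they give opposite verdicts on 39 to 44 enrollments from 60 eligible families, and on follow-up as well

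*Combined protocol and SAP*

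**What the plan says.** **Pass rule, first form.** Section 2.2 (H2a) says feasibility is shown by a 75% recruitment rate and 80% follow-up survey collection per arm. Section 8.1 defines it as consent to randomization of 75% or more, with attrition of no more than 20% per arm.

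**Pass rule, second form.** Section 11.0 says: "Feasibility will be established if the upper bound of the CI contains 75% and 80% for consent and follow-up respectively". The intervals are 90%. The worked consent benchmark is "With an estimated 60 eligible patients at 6 months, at least 39 (65%; 90% CI 53.6-75.2%) need to enroll". The follow-up benchmark is 28 of 40 randomized patients (70%; 90% CI 56.0-81.7%), pooled over arms. Completion by arm is also to be estimated, but with no pass mark.

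**Accrual.** Section 11.0 forecasts 84 eligible families a year at DFCI and 36 at UAB, and continues: "We estimate a 75% consent rate for a total possible annual sample size of N=90 patients". It then plans: "Forty patients will be accrued over 6-months at DFCI (n=28) and UAB (n=12").

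**End of enrollment.** Section 4.0 gives a number, "The target sample size is 40 participants", with firm site wording ("At DFCI, a total of 28 participants will be enrolled and randomized"). It also gives a period: "Families will be recruited consecutively at each site over a 6-month time period". Appendix D, Accrual Monitoring, sets a different period for UAB: "Enrollment of 12 participants over 12 months".

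**The concern.** Consent and follow-up together make up the primary endpoint. An observed rate of at least 75% is a different requirement from an upper confidence limit of at least 75%. The second can be met by a rate well below 75%, and more easily the smaller the sample. If both stay in the plan, a result between the two thresholds can be reported as feasible or as not feasible, and the choice could be made after the data are seen. The decision on a definitive multi-center trial would draw on that verdict.

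The open closing condition adds a second ambiguity. The consent rate depends on which eligible families are counted. If enrollment closes on a number while the denominator runs on to a date, families who were never asked would lower the rate as if they had declined.

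**Working it through.** **Inputs.** Section 11.0: 84 + 36 = 120 eligible a year, so 60 in 6 months; assumed consent 75%; 40 planned (28 + 12); 90% intervals. Sections 2.2 and 8.1: 75% consent; 80% follow-up per arm. The arm size of 20 follows from 1:1 randomization of 40.

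**1. The plan's own figures.** The exact (Clopper-Pearson) two-sided 90% limits for x of n are the 5% quantile of Beta(x, n−x+1) and the 95% quantile of Beta(x+1, n−x).
- 39/60: 53.6-75.2%, as stated. 38/60 has an upper limit of 73.7%, so 39 is the right minimum.
- 28/40: 56.0-81.7%, as stated. 27/40 has an upper limit of 79.6%, so 28 is the right minimum.

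**2. Consent under the two rules, 60 families counted.**
- Point estimate: 0.75 × 60 = 45 needed.
- Upper limit: 39 needed.
- Results from 39 to 44 pass the second and fail the first. Example: 40/60 = 66.7%, CI 55.4-76.7%.

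Pass probabilities, X ~ Binomial(60, p), independent families, no cap on enrollment:

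| True consent p | Point rule, P(X ≥ 45) | Upper-limit rule, P(X ≥ 39) |
|---|---|---|
| 0.60 | 0.01 | 0.26 |
| 0.65 | 0.07 | 0.56 |
| 0.70 | 0.24 | 0.84 |
| 0.75 | 0.57 | 0.97 |

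**3. Follow-up under the two rules.**
- Pooled, 40 randomized: the point rule needs 0.80 × 40 = 32; the upper-limit rule needs 28. Results from 28 to 31 get opposite verdicts.
- Per arm, 20 randomized: the point rule needs 0.80 × 20 = 16 in each arm. The upper-limit rule would need 13 (13/20 has an upper limit of 82.3%; 12/20 has 78.3%).
- A pooled pass can hide an arm that fails: 28/40 could be 18/20 and 10/20.

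**4. Closing condition.**
- Expected enrollments in 6 months: 60 × 0.75 = 45, against 40 planned.
- Families needed for 40 enrollments: 40/0.75 = 53.3. At 10 a month that is about 5.3 months.
- If enrollment stopped at 40 and all 60 were counted, the rate could be at most 40/60 = 66.7%; by site, 28/42 and 12/18 are also 66.7%. Section 8.1's 75% could not then be met.
- With 40 enrolled, both rules pass for a denominator of 53 or fewer (40/53 = 75.5%). They disagree from 54 to 61, and both fail from 62 (40/62 has an upper limit of 74.6%).

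**The case against.** **Section 11.0 may simply make 8.1 operational.** This is the best defense. A pilot may reasonably ask only that its data be compatible with the target, and the analysis section is where such a rule belongs. But no section says that 11.0 governs, and 8.1 states a minimum consent rate, which is a different criterion.

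**The arithmetic is sound.** This stands. Both intervals and both minimum counts are right. A reader might infer an arithmetic error from 45 expected against 40 planned. The documents do not support that: Section 11.0 calls 90 a year the total possible, and planning 40 where about 45 could be had is ordinary headroom. The minimum of 39 is also reachable within 40.

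**The 66.7% ceiling is hypothetical.** This also stands. A reader might infer that the plan has made its 75% target unreachable. That needs a hard stop at 40 and a count that includes families never asked, and the documents state neither. Sixty is an estimate, and 40 of 60 appears nowhere as a planned result. Given such a stop, the chance that more than 40 families would consent is 0.91 with exactly 60 eligible at 75% consent, but 0.77 if the number eligible varies binomially at the plan's own rates (210 × 20% and 60 × 30% in 6 months).

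**The 12 months for UAB is a site-performance expectation.** Fair: it is not an analysis window, and Section 8.1's timeline also shows 6 months for enrollment. It still needs to be reconciled with Section 4.0.

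**Conclusion.** The conflict between the two rules is real and lies between Sections 2.2 and 8.1 on one side and Section 11.0 on the other. It does not depend on any cap. With 60 eligible families the thresholds are 45 and 39. With 40 randomized they are 32 and 28 pooled, and it is unclear whether follow-up is judged pooled or per arm. The rules differ greatly in stringency: at 65% true consent, ten points below target, one passes 7% of the time and the other 56%. These probabilities assume exactly 60 families, independent decisions and a constant consent rate.

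The closing condition is a secondary gap. Section 11.0 names eligible patients at 6 months as the base, but no section says whether the number or the period ends enrollment, or which eligible families count after that. The 66.7% ceiling applies only under the conditional reading described above. The point should be settled before analysis; it does not call for a change in sample size or design.

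**What to change.** 1. **One rule.** State it in the same words in Sections 2.2, 8.1 and 11.0, for consent and follow-up. Either use the point estimate (at least 75% and at least 80%) with its 90% CI reported, or require the upper limit of the 90% CI to be at least 75% and 80%. Do not word the second option as the interval not excluding the target: 51/60 = 85% has a CI of 75.3-91.9%, and such wording would fail it for being too high. Say whether follow-up is judged per arm or pooled, and give the chosen rule's pass probabilities over a range of true rates, as in the table above.

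2. **Closure and denominator.** Say whether 40 (28/12) or a fixed period closes enrollment, and reconcile 6 months in Sections 4.0 and 11.0 with 12 months for UAB in Appendix D. Use as the consent denominator all eligible families identified up to closure, by site if sites close separately. Include those not approached, or declined by the provider, while enrollment was open, since Section 5.1 itself names gate-keeping as a concern. Exclude families who become eligible after closure. Report consent among approached families beside it.

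**Cost.** Wording in Sections 2.2, 4.0, 8.1 and 11.0 and the UAB accrual line in Appendix D, plus a record for each eligible family of whether and when the study was offered and what was decided. Appendix D already lists screening logs for all sites, so this may be only an added field; the documents do not say what the logs hold.

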We will actively retain families in this study by utilizing ongoing face-to-face study team contact to maintain engagement as well as modest remuneration for ongoing participation. Participants will not be expected to experience any economic burden as part of this study. Enrolled families will receive small (\$50 Amazon gift card) remuneration to off-set the cost of their time participating in baseline and follow-up surveys (total value \$100 if complete both surveys). Prior non-interventional survey-based studies of HMH by our group have demonstrated excellent retention over time.

Due to the relatively low-participant burden, modest remuneration, and patient-centered nature of the intervention we do not anticipate problems with recruitment and retention.

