Enrolled participants will be randomized 1:1 by site to receive either the PediCARE intervention or UC for a duration of 6-months.

Participants will be randomly assigned to PediCARE or UC with a 1:1 allocation by site as per a computer-generated randomization sequence created by the study statistician. Sequences will be embedded in REDCap by informatics personnel. This approach to randomization will allow for real-time randomization of participants. Study personnel will not have access to the sequences. After randomization, participants and study team will be unblinded to group assignment as the intervention is not amenable to blinding.

9.3 Intervention Procedures:

The PediCARE study will pilot direct resource provision (groceries and transportation) to households of children newly diagnosed with cancer with a goal of reducing a concrete measure of poverty, household material hardship (HMH).

9.3.1 Usual Care (UC) Components (Control): UC psychosocial support in pediatric cancer is institution-specific but routinely includes (1) a psychosocial clinician available as part of the cancer care team; (2) social work screening for social and financial needs including such examples as insurance coverage and eligibility for Institutional, community or private cancer foundation supports; (3) social work assistance with applications on a case by case basis for insurance (i.e. Medicaid) and community/institutional/private financial supports; and (4) provision of parking vouchers and/or limited gift cards (e.g. cafeteria and hospital-retail food) when available.

9.3.2 PediCARE Intervention Components: PediCARE includes direct resource provision in two domains: Food and Transportation. Resource provision will be centrally administered by DFCI.

(1) **Food:** Families will receive a monthly pre-paid allocation of Instacart funds for grocery purchasing and delivery in a dollar amount adapted from the March 2018 U.S. Department of Agriculture's (USDA) Thrifty Food Plan (see Appendix B) for family size (e.g. family of 4 with two toddlers will receive \$640; cost range based on family sizes of 2-7 people and capped at 7 people). The Thrifty USDA Food Plan serves as the national standard for a nutritious diet at a minimal cost and is used as the basis for maximum SNAP benefit (e.g. food stamp) allotments, as such it represents a valid bench-mark for household food costs.

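### Follow-up feasibility is defined per arm in Sections 2.2 and 8.1, but the only pass mark in Section 11 is pooled (28/40), so one arm can fail the plan's own criterion while feasibility is declared

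*Combined protocol and SAP*

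**What the plan says.** Two sections define the follow-up criterion by arm. In Section 2.2, H2a reads "Feasibility will be demonstrated by recruitment rate of 75% and follow-up survey data collection of 80% per arm". Section 8.1, which names feasibility as the primary endpoint, reads "Feasibility will be defined as at least 75% consent to randomization and at most 20% attrition per arm".

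Section 11 (Analysis Plan) turns this into a decision rule: "Feasibility will be established if the upper bound of the CI contains 75% and 80% for consent and follow-up respectively". That sentence names no arm. The only follow-up threshold worked out from it is pooled: "With an estimated 40 randomized patients, at least 28 (70%; 90% CI 56.0-81.7%) need to have complete 6-month data". Section 11 then adds that completion will also be estimated with a 90% CI in each arm, without a threshold or consequence. Section 8.1 treats arm differences in the same descriptive way: "We will assess process barriers to feasibility including recruitment, attrition by arm and parent report of PediCARE component utilization".

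**The concern.** The endpoint is per arm and the only operational pass mark is pooled, so the same data can give two verdicts. With 18/20 in one arm and 10/20 in the other, 28/40 meets Section 11, while 50% attrition in one arm fails Section 8.1. Nothing says which section prevails, so the verdict could be settled after the data are seen.

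This concerns the primary endpoint of a pilot whose purpose is to support a definitive randomized trial. Unequal loss between arms is the kind of attrition most likely to bias that trial's comparison, and a pooled rate can mask it. It is plausible here. Section 9.2 says "After randomization, participants and study team will be unblinded to group assignment as the intervention is not amenable to blinding", and only one arm receives groceries and transport. The reassurance in Section 5.4, "Prior non-interventional survey-based studies of HMH by our group have demonstrated excellent retention over time", comes from studies without an intervention and does not address differences between arms.

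**Working it through.** **Inputs.** Arm size: Section 4.0 plans 14 + 6 = 20 per arm. Target 80%, two-sided 90% CI, upper-bound rule and pooled mark 28/40: Section 11. The true completion rates below are assumptions; the documents give none.

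**1. Reproduce the plan's figure.** Section 11 does not name the interval for the feasibility rates, so I tried the exact (Clopper-Pearson) one. For x completers of n, the lower limit is the 5% quantile of Beta(x, n−x+1) and the upper limit is the 95% quantile of Beta(x+1, n−x).

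- 28/40: 56.0–81.7%, as printed.
- 27/40: 53.4–79.6%, which excludes 80%.

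So 28 is the correct pooled minimum. Wilson (57.1–80.3%) and Wald (58.1–81.9%) do not match the printed limits.

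**2. Apply the same interval within an arm of 20.**

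| Split giving 28/40 | Weaker arm | Its exact 90% CI | Reaches 80%? |
|---|---|---|---|
| 14 + 14 | 14/20 | 49.2–86.0% | yes |
| 15 + 13 | 13/20 | 44.2–82.3% | yes |
| 16 + 12 | 12/20 | 39.4–78.3% | no |
| 17 + 11 | 11/20 | 34.7–74.1% | no |
| 18 + 10 | 10/20 | 30.2–69.8% | no |
| 19 + 9 | 9/20 | 25.9–65.3% | no |
| 20 + 8 | 8/20 | 21.7–60.6% | no |

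Five of the seven splits pass the pooled mark while one arm's CI excludes 80%. Observed attrition of 50% in one arm passes if the other arm retains at least 18/20; 60% passes only if the other retains 20/20. Such cases continue up to 20 + 12 = 32/40.

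The reverse also occurs. 13 + 13 = 26/40 and 13 + 14 = 27/40 pass in each arm but fail pooled (upper bounds 77.4% and 79.6%).

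**3. Pass probabilities.** Let X₁ and X₂ be independent Binomial(20, p₁) and Binomial(20, p₂). Current rule: P(X₁+X₂ ≥ 28). Amended rule: P(X₁+X₂ ≥ 28, X₁ ≥ 13, X₂ ≥ 13).

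| Assumed true completion | Current | Amended |
|---|---|---|
| 80% / 80% | 95.7% | 92.2% |
| 65% / 65% | 31.4% | 26.4% |
| 90% / 80% | 99.6% | 96.7% |
| 85% / 75% | 95.8% | 88.3% |
| 90% / 75% | 98.6% | 89.6% |
| 80% / 70% | 82.2% | 71.0% |
| 85% / 70% | 90.8% | 75.5% |
| 85% / 60% | 71.5% | 40.1% |
| 90% / 60% | 83.6% | 41.4% |
| 80% / 50% | 30.4% | 11.3% |
| 85% / 50% | 43.3% | 12.6% |
| 90% / 50% | 58.1% | 13.1% |
| 95% / 50% | 73.3% | 13.2% |

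The gap between columns is the probability of a pooled pass with at least one arm's CI excluding 80%: for 90%/60%, 83.6 − 41.4 = 42.2 points.

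**4. Alternatives.** The per-arm condition alone passes 36.1% of the time at 65%/65%, more than the pooled rule's 31.4%, so it should not replace the pooled mark. A literal 16/20 in each arm passes only 39.6% of the time when both arms are truly at 80%.

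**The case against.** The rule sentence in Section 11 names no population, and by-arm CIs at the same 90% level are planned in the same paragraph. Read with Section 8.1, the 80% test could be meant for those intervals, with 28/40 as an overall illustration. That reading is possible, but it leaves the per-arm mark (13/20) unwritten, so the text still needs correcting.

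The large drops in pass probability need a 25-point or wider gap in true completion. For the 10- to 15-point gaps tabulated, the drop is about 3 to 15 points. That stands, and the size of the problem depends on an imbalance nobody can yet know. The plan also has safeguards common to both arms: the same payment for the follow-up survey, reminders, telephone, video or paper completion, and monitoring of retention by the DSMC. These make imbalance less likely; they do not settle the verdict if it occurs.

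Pooling is not the only gap between the sections. 14/20 in each arm meets Section 11 yet shows 30% attrition per arm, which fails Section 8.1 read literally. That difference is point estimate versus upper confidence bound. It also stands, and is why 2.2 and 8.1 need rewording whichever rule is chosen.

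Finally, this is a 40-family pilot and by-arm rates will be reported regardless, so planners would see an imbalance. True, but reporting it does not say whether the primary endpoint was met.

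**Conclusion.** The concern holds. The printed 28/40 is arithmetically correct but is applied to the pooled sample for an endpoint defined per arm, and no text resolves the conflict. Feasibility of follow-up can be declared with an arm as low as 8/20. The probability of a pooled pass with a failing arm is 3.5% if both arms are at 80%, about 3 to 15% for the moderate gaps shown, and about 19 to 60% when one arm is at 50–60% and the other at 80–95%.

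This rests on 20 per arm as planned, independent outcomes, the exact interval (inferred because it reproduces the printed limits) and assumed true rates. It covers follow-up only; overall feasibility also needs the consent criterion. It should be fixed before the data are analysed.

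**What to change.** In Section 11, keep the pooled 28/40 condition and add: *and, in each arm, the upper bound of the exact 90% CI for 6-month completion is at least 80%*. With 20 per arm this means at least 13/20. If arm sizes differ, the minimum is 11/18, 12/19, 14/21 or 14/22. State that the interval is Clopper-Pearson. Reword 2.2 and 8.1 so that the per-arm criterion refers to this CI-based rule.

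Making 2.2 and 8.1 explicitly pooled, with by-arm rates descriptive, would also remove the contradiction, but would give up the per-arm protection those sections now state. If the sponsor prefers that, it should be a declared choice.

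The cost is one added condition and matching wording; the by-arm CIs are already planned, and no extra data or families are needed. The pass probability when both arms are truly at 80% falls from 96% to 92%. At 20 per arm the added condition is lenient: it tolerates 7/20 = 35% observed attrition in one arm. It screens out gross imbalance and does not demonstrate 80% completion in each arm.
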